#### **6.10.2.1. Reduction of Liver Fat Assessed by MRI-PDFF at 6 Weeks**

The reduction of liver fat assessed by MRI-PDFF at 6 Weeks will be analyzed similar to the primary preliminary efficacy endpoint.

A supportive analysis using a mixed effects model with repeated measures (MMRM) will be used to analyze the change from baseline, both absolute change and percent change (absolute and relative), to week 6 and week 12; the model will include change in liver fat (%) on MRI-PDFF (absolute and relative) as dependent variable, treatment group as independent variable, covariates including baseline liver fat (%), visit, interaction term of treatment and visit, and a random slope and intercept per subject. Model parameters will be estimated using the restricted maximum likelihood method (REML). An unstructured covariance matrix will be used to estimate the intercept-slope covariance. In case of convergence problem, other covariance structure will be used in the order of compound symmetry and variance component. The least squares (LS) means and their corresponding 90% confidence intervals and p-values at one sided test will be presented. The LS mean difference between treatment groups will be presented along with the 90% confidence interval and p-value.

The following SAS code will be used for the MMRM analysis:

```
Proc mixed method=reml;
  Class usubjid visit treat;
  Model change [or percentchange] = baseline visit treat
  treat*visit /ddf=kr solution alpha=0.05;
  repeated visit /subject=usubjid type=un;
Run;
```

Where treat=treatment group (pooled placebo, FT4101 3.0 mg, FT 4101 4.5 mg), baseline = baseline liver fat (%), change = absolute change in liver fat (%) from baseline, percentchange = relative percent change in liver fat (%) from baseline, visit=study visit (Week 6, Week 12), usubjid = subject ID.

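### The mixed-model fallback, applied to the printed REPEATED code, forces equal visit variances and finally zero within-subject correlation; if it is reached, standard errors can be wrong in either direction

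*SAP*

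**What the plan says.** Three SAP sections use the same mixed-model wording: 6.10.2.1 (liver fat, Weeks 6 and 12), 6.10.2.3 (liver biochemistry, Weeks 6, 11 and 12) and 6.10.3.1 (fasting hepatic DNL, post-dose samples at C4D4, C4D8, C4D15 and C4D22). Each gives the model a subject-level random part, "and a random slope and intercept per subject", and continues: "An unstructured covariance matrix will be used to estimate the intercept-slope covariance". The fallback sentence comes next: "In case of convergence problem, other covariance structure will be used in the order of compound symmetry and variance component".

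Section 6.10.2.1 then prints the SAS code to be used. It has no RANDOM statement. Its only covariance statement is "repeated visit /subject=usubjid type=un". The fixed effects include the full interaction, with Kenward-Roger degrees of freedom: "treat*visit /ddf=kr solution alpha=0.05". No empirical (sandwich) standard error is requested. Section 6.10.3.1 refers back to this code. Section 6.10.2.3 refers to a Section 7.3.2.1, which the SAP does not contain; 6.10.2.1 is presumably meant.

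On reporting, 6.10.2.1 says: "The least squares (LS) means and their corresponding 90% confidence intervals and p-values at one sided test will be presented". It does not say whether the treatment difference is per visit or averaged over visits, and the code has no LSMEANS or ESTIMATE statement to settle it. Sections 6.10.2.3 and 6.10.3.1 ask for differences at each post-baseline visit. The liver-fat model is introduced as secondary to the Wilcoxon test: "A supportive analysis using a mixed effects model with repeated measures (MMRM) will be used to analyze the change from baseline". The protocol names no covariance structure, so the fallback is a matter for the SAP alone.

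**The concern.** On the REPEATED statement, `type=cs` allows one variance and one covariance, and `type=vc` allows one variance and no covariance. At the last step, two to four readings from one person are therefore analysed as if they came from different people with equal spread. Kenward-Roger does not repair a wrong covariance structure, and no robust standard error is in place.

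The rule is fixed in advance, so analysts who reached it would be following the plan. What is at stake is the accuracy of the intervals and p-values for the supportive liver-fat model, the secondary enzyme models and the exploratory DNL model. A second loss concerns missing data. SAP 6.1.6 imputes no efficacy data, so in these models the between-visit correlation is the only route by which an earlier reading informs a missing later one. Variance component closes that route.

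**Working it through.** **Inputs.** From SAP 3.4: 10 subjects per dose group, 10 pooled placebo, SD 14. Nominal one-sided error 5%, the tail that matches the 90% intervals. Visits as listed above. Assumed, because neither document gives them: between-visit correlation ρ and any change of SD between visits. True effect zero. The SAP states no figure for these models, so there is none to reproduce; the 84% power in 3.4 belongs to the Wilcoxon test and is not used here.

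Variance component on REPEATED is ordinary least squares on the stacked visits. It was simulated that way with baseline and treatment-by-visit cells (8,000 runs per two-visit setting; Monte Carlo error √(0.05×0.95/8000) = 0.24 points).

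**1. Single-visit difference, equal SDs.** The comparison is between different subjects, so ignoring within-subject correlation costs little. The true SE is 14×√(2/10) = 6.26, and the model SE in simulation at ρ = 0.5 is also 6.26. Simulated error is 5.0 to 5.3% for ρ from 0 to 0.7 and 5.6 to 5.8% at ρ = 0.9. With three visits it is 5.4 to 5.8% for ρ of 0.5 to 0.7. The inflated degrees of freedom (60−7 = 53 against 30−4 = 26) change the critical value only from 1.706 to 1.674, or 1.9%.

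**2. Average of two visits, equal SDs.** The true variance carries a factor (1+ρ)/2 and variance component uses 1/2, so model SE/true SE = 1/√(1+ρ). Approximate error is 1−Φ(1.674/√(1+ρ)).

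| ρ | SE ratio | Approx. error | Simulated error | 90% CI coverage |
|---|---|---|---|---|
| 0.3 | 0.877 | 7.1% | 7.7% | 85% |
| 0.5 | 0.816 | 8.6% | 8.8% | 82.5% |
| 0.7 | 0.767 | 10.0% | 10.5% | 80% |
| 0.9 | 0.725 | 11.2% | 12.5% | 76% |

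**3. Single visit, unequal SDs.** The model uses one pooled SD, √((s₆²+s₁₂²)/2).
- SDs 10 and 14: pooled √148 = 12.17. SE ratio is 12.17/10 = 1.217 at Week 6 and 12.17/14 = 0.869 at Week 12. Approximate errors are 2.1% and 7.3%; simulated at ρ = 0.5, 2.6% and 7.4% (coverage 94.6% and 84.4%).
- SDs 7 and 14: pooled √122.5 = 11.07. Ratios are 1.581 and 0.791; simulated errors 0.7% and 9.4%.

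Compound symmetry also pools the variance, so the first fallback step shares this problem, although it keeps the correlation.

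**4. Four DNL visits.** The samples fall 3, 7, 14 and 21 days after labelling starts, and labelled water is taken only to C4D7 (Protocol 8.5.1), so changing spread is plausible. With assumed relative SDs 0.6, 0.8, 1 and 1, the pooled value is √((0.36+0.64+1+1)/4) = 0.866. The SE ratio is 0.866/0.6 = 1.443 at C4D4 and 0.866 at C4D15 and C4D22. Simulation at ρ = 0.7 gave 1.3 to 1.4% error at C4D4 and 7.9 to 8.8% at the last two visits.

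**5. Change between two visits, equal SDs.** The ratio is 1/√(1−ρ), which is 1.41 at ρ = 0.5. The SE is too large and the test conservative.

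**6. If the text governs instead of the code.** Variance component on the random effects only makes intercept and slope uncorrelated; the visits stay correlated. For example, with intercept SD 10, slope SD 0.5 per week and residual SD 5, the Week 6 and Week 12 variances are 100+36×0.25+25 = 134 and 100+144×0.25+25 = 161, and the covariance is 100+72×0.25 = 118. The correlation is 118/√(134×161) = 0.80.

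**7. How likely the trigger is under the printed code.** Unstructured has v(v+1)/2 parameters: 3 for two visits, 6 for three, 10 for four. Compound symmetry, with two parameters, must then also fail before variance component is used.

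**The case against.** The strongest reply is that the fallback sentence follows directly on the one about the intercept-slope covariance. Read in place, it concerns the random-effects matrix, where variance component does not make visits independent (step 6). This stands as a limit: the point holds for the printed code, and the SAP must say which model it means. It does not dispose of the point, because the SAP commits to code that has no random effects.

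The second reply concerns direction. A reader might infer that the fallback makes these intervals and p-values too optimistic in general. The documents do not support that. With treatment-by-visit in the model, single-visit differences are about right when variances are equal, and less variable visits and between-visit changes become conservative. Nor should a three-visit average be cited against the enzyme model. Its simulated error of 13.0 to 14.4% at ρ of 0.5 to 0.7 is real arithmetic, but 6.10.2.3 reports differences per visit. Averaging is a live reading only in 6.10.2.1, where the contrast is unnamed.

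Third, the trigger is remote with two visits, and the consequence is small. The primary analysis is a Wilcoxon test with Holm adjustment, the liver-fat model is supportive, and DNL is exploratory with its own Wilcoxon test. All of that stands. A higher chance of reaching the fallback with four DNL visits and missing data is plausible from the parameter count, but it has not been calculated.

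**Conclusion.** The point holds conditionally and is a low-priority improvement. If the fallback is reached and applied to REPEATED, compound symmetry and variance component impose equal variances, and variance component also removes within-subject correlation. Standard errors are then:
- too small for a visit-averaged difference under variance component (error about 8 to 12% for ρ of 0.3 to 0.9);
- too small at the more variable visits (about 7 to 9% in the SD patterns tried);
- too large at the less variable visits (about 1 to 3%);
- about right for single-visit differences with equal variances.

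Variance component also stops earlier visits from informing missing later ones; the resulting bias was not quantified. Every size above rests on assumed correlations and SD patterns and is conditional on the fallback being used. The primary efficacy test does not change.

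**What to change.** In SAP 6.10.2.1, 6.10.2.3 and 6.10.3.1:
- State that the covariance structure and its fallback apply to the visit (REPEATED) covariance, and bring the random-slope text and the code into line. Correct the code cross-reference in 6.10.2.3.
- Delete variance component.
- For the three-visit enzyme models and the four-visit DNL model, fall back from unstructured to heterogeneous compound symmetry. For any structure other than unstructured, use an empirical (sandwich) standard error with a small-sample correction. Visit-indexed Toeplitz or autoregressive structures suit these schedules less well, because the visits are unevenly spaced (for example Weeks 6, 11 and 12).
- For the two-visit liver-fat model, heterogeneous structures have two variances and one correlation and so equal unstructured. If unstructured fails, go straight to a baseline-adjusted ANCOVA at each visit.
- State in 6.10.2.1 that the LS mean difference is reported per visit.

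The cost is a few sentences and a little extra code for the sandwich and ANCOVA branches. Intervals would differ slightly if a fallback were used. Per-visit ANCOVA has a limitation of its own: it does not borrow from other visits when data are missing.

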#### **6.10.2.2. Proportion of Subjects with $\geq 30\%$ Relative Reduction in Liver Fat at Week 12 Assessed by MRI-PDFF**

The proportion of subjects experiencing a relative reduction of 30% or greater of liver fat at week 12 as assessed by MRI-PDFF will be summarized descriptively and analyzed using a Fisher's exact test. Subjects in each dose group will be compared to the pooled placebo subjects

from each cohort. P-values will be corrected using Holm's Sequential Bonferroni procedure as previously described.

#### 6.10.2.3. Reduction of Liver Biochemistry Markers

Liver biochemistry markers and the change from baseline will be summarized descriptively by visit and cohort and treatment group. A MMRM will be used to analyze the change from baseline to Week 6, Week 11, and Week 12; the model will include change from baseline as dependent variable, treatment group as independent variable, baseline and visit and interaction term of treatment and visit as covariates, and a random slope and intercept per subject. Model parameters will be estimated using REML. An unstructured covariance matrix will be used to estimate the intercept-slope covariance. In case of convergence problem, other covariance structure will be used in the order of compound symmetry and variance component. The LS mean and standard error and its corresponding 90% confidence intervals and p-values will be presented for each post-baseline visit. The LS mean difference between treatment and placebo will be presented along with its 90% confidence interval and the p-value for each post-baseline visit. Similar SAS code as described in Section 7.3.2.1 will be used.

Each liver biochemistry marker (mean  $\pm$  SD) will be also plotted over time by treatment group using line plot.

#### 6.10.3. Analysis of Exploratory Pharmacodynamic Endpoints

In general, analysis of exploratory PD endpoints will be descriptive.

The exploratory PD endpoints are:

- Change from baseline in fasting hepatic DNL
- **Sebumeter®:**
  - Change from baseline in total sebum production
- **Sebutape®:**
  - Change from baseline in sebum free fatty acid concentrations
  - Change from baseline in sebum DNL
- **Circulating Biomarkers of Liver Injury and Fibrosis:**
  - Change from baseline in ELF score: Hyaluronic acid (HA), Procollagen III amino terminal peptide (PIIINP), Tissue inhibitor of metalloproteinases 1 (TIMP-1)
  - Change from baseline in Cytokeratin-18 (CK-18) fragments, e.g., CK-18 M30 and CK-18 M65
  - Change from baseline in FibroSure®
  - Change from baseline in PRO-C3
- **Circulating Metabolic Parameters:**
  - Change from baseline in fasting lipids:
    - Total cholesterol
    - Low-density Lipoprotein cholesterol (LDL-c) direct
    - High-density Lipoprotein cholesterol (HDL-c)
    - Non-HDL cholesterol (non-HDL-c)

- Triglycerides (TG)
- Free fatty acids (FFA)
- Change from baseline in glycemic parameters:
  - Fasting plasma glucose (FPG)
  - Fasting insulin
  - HOMA-IR
  - HbA1c
- Change from baseline adiponectin (total and high molecular weight)
- Change from baseline in FGF-21
- Change from baseline in malonyl carnitine
- **FibroScan®:**
  - Change from baseline in CAP
  - Change from baseline in LSM
- **MRI-PDFF:**
  - Change from baseline in liver volume
  - Change from baseline in liver fat volume index

#### **6.10.3.1. Change from Baseline in Fasting Hepatic De Novo Lipogenesis**

Multiple blood samples will be collected at C1D-11, C1D-7, and C1D1 and post-dose at C4D4, C4D8, C4D15, and C4D22 to measure deuterium enrichment in plasma body water and plasma triglyceride-palmitate. Fractional DNL will be determined by the quantification of newly synthesized palmitate through the DNL pathway in blood sampled in the fasting state after two weeks labeling period.

Fractional hepatic DNL (%) and its absolute and percentage changes from baseline will be summarized by visit and treatment group. P value from one-sided Wilcoxon-Mann-Whitney test at significance level of 0.05 will be provided. In addition, the change from C4D15 to C4D22 will be presented to evaluate rebound of DNL.

A MMRM model will be used to analyze the absolute change in fraction of fasting hepatic DNL from baseline; the model will include change in fraction of fasting hepatic DNL from baseline as dependent variable, treatment group as independent variable, baseline fraction of fasting hepatic DNL and visit and interaction term of treatment and visit as covariate, and a random slope and intercept per subject. Model parameters will be estimated using REML. An unstructured covariance matrix will be used to estimate the intercept-slope covariance. In case of convergence problem, other covariance structure will be used in the order of compound symmetry and variance component. The LS mean and standard error and its corresponding 90% confidence intervals and p-values will be presented for each post-baseline visit. The LS mean difference between treatment and placebo will be presented along with its 90% confidence interval and the p-value for each post-baseline visit. Similar SAS code as described in Section 6.10.2.1 will be used.

Line plots of the fraction of fasting hepatic DNL (mean  $\pm$  SD) will be plotted over time by treatment group for both pre-dose (C1D-11, C1D-7, and C1D1) and post-dose (C4D4, C4D8, C4D15, and C4D22); they will be overlaid to allow visual comparison.

#### **6.10.3.2. Skin Surface Sebum Level Using Sebumeter®**

Observed values and the change from baseline of total sebum production will be summarized by visit and treatment group.

#### **6.10.3.3. Sebum FFA and Sebum DNL Using Sebutape®**

Observed values and the change from baseline in FFA collected using Sebutape® will be summarized by visit and treatment.

Observed values and the change from baseline in the Sebum DNL collected using Sebutape® will be summarized by visit and treatment.

#### **6.10.3.4. Circulating Biomarkers of Liver Injury and Fibrosis**

Observed values and the change from baseline of circulating biomarkers of liver injury and fibrosis will be summarized by visit and treatment group.

#### **6.10.3.5. Circulating Metabolic Parameters**

Observed values and the change from baseline of circulating metabolic parameters will be summarized by visit and treatment group.

#### **6.10.3.6. Steatosis (CAP) and Liver Stiffness (LSM) Determined by FibroScan®**

Observed values and the change from baseline of CAP and LSM will be summarized by visit and treatment group.

#### **6.10.3.7. Imaging Parameters Assessed by MRI-PDFF**

Observed values and the change from baseline of liver volume and liver fat volume index will be summarized by visit and treatment group.

Liver fat volume index is calculated as PDFF(%) multiplied by Liver Volume (L).

### **6.11. Analysis of Safety Endpoints**

The primary safety endpoints are:

- Incidence of treatment-emergent adverse events (TEAEs)
- Incidence of clinical lab abnormalities
- Incidence and severity of clinical findings on physical examination
- Change from baseline in vital signs (blood pressure [BP], heart rate [HR], respiratory rate, and temperature)
- Change from baseline in 12-lead electrocardiogram parameters (HR, QT interval, PR interval, QRS interval, RR interval, and QTc [corrected] using the Fridericia correction

[QTcF = QT/cubic root of the R-R interval, where R-R is the duration of the entire cardiac cycle])

### **6.11.1. Analysis of Primary Safety and Tolerability Endpoints**

#### **6.11.1.1. Adverse Events**

The latest version of the Medical Dictionary for Regulatory Activities (MedDRA version 22.0) will be used to code adverse events (and medical history). TEAEs will be summarized by treatment group. TEAE is defined as an adverse event with an onset that occurs after receiving the first dose of the study drug (AE start date  $\geq$  first dose date) and within 30 days after receiving the last dose of the study drug (AE start date – last dose date  $\leq$  30). TEAEs will be tabulated including the following categories:

- TEAEs by System Organ Class and Preferred Term.
- Drug-related TEAEs by System Organ Class and Preferred Term. Related includes: Definitely Related, Possibly Related, or Probably Related; Unrelated includes: Not Related or Unlikely to be related. If drug relationship is missing, event will be considered related to the study drug.
- TEAEs Leading to Discontinuation of Study Drug by System Organ Class and Preferred Term.
- Serious TEAEs by System Organ Class and Preferred Term.
- Drug-related Serious TEAEs by System Organ Class and Preferred Term.
- Serious TEAEs Leading to Discontinuation of Study Drug by System Organ Class and Preferred Term.
- Severity of TEAEs by System Organ Class and Preferred Term. Severity of TEAEs will be presented using National Cancer Intuitive Common Toxicity Criteria for Adverse Events (CTCAE) grade. Subjects with same AE more than once will have the maximum CTCAE grade counted within system organ class and preferred term.

In each AE summary table above, subjects with same AE more than once will be counted only once within the same system organ class and preferred term.

An overall summary TEAE table will be also provided to present number and percentage of subjects who had any TEAE, drug-related TEAE, CTCAE grade 3 or higher AE, CTCAE grade 3 or higher drug-related TEAE, serious TEAE, drug-related serious TEAE, TEAE leading to drug discontinuation, TEAE leading to on-study death. On-study death is defined as death as the death that occurs between the first date of study drug and within 30 days after the last date of study drug.

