### 10.1 Definitions

#### 10.1.1 Adverse Event (AE)

An AE is any undesirable and unintended medical event occurring to a subject in a clinical study, whether or not related to the study products. This includes events from the first study related activity after the subject has signed the informed consent and until post treatment follow-up period as defined in the protocol. The following should not be recorded as AEs, if recorded as medical history/concomitant illness on the CRF at screening:

- Pre-planned procedure, unless the condition for which the procedure was planned has worsened from the first study related activity after the subject has signed the informed consent
- Pre-existing conditions found as a result of screening procedures
- Pre-existing events that has not worsened in intensity or frequency from baseline.

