#### 10.1.2 Treatment emergent Adverse Event (TEAE)

- A TEAE is defined as any untoward medical occurrence in a subject administered a medicinal product that does not necessarily have a causal relationship with this treatment.
- A TEAE can, therefore, be any unfavorable and unintended sign (including an abnormal laboratory finding), symptom, or disease temporally associated with the use of an investigational product, whether or not related to the investigational medicinal product.
- This includes an exacerbation of pre-existing conditions or events, intercurrent illnesses, drug interaction, or the significant worsening of the indication under

investigation that is not recorded elsewhere on the eCRF under specific efficacy assessments.

Anticipated fluctuations of pre-existing conditions that do not represent a clinically significant exacerbation or worsening are not considered AEs.

If progression of the underlying disease (i.e., the condition being treated with study drug) might be reasonably anticipated given the nature and severity of the underlying disease, then progression of the underlying disease per se will not constitute an AE. However, if the progression of the underlying disease meets the criterion for “serious” categorization of AEs (e.g., the underlying disease results in death or hospitalization, etc.), then the progression of underlying disease should be reported as an SAE.

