#### **10.2 Recording of Adverse Events and Serious Adverse Events**

- Any AE that occurs after signing of ICF through 28 days after last dose of study drug(s) should be recorded on the AE eCRF.
- In order to avoid vague, ambiguous, or colloquial expressions, the AE should be recorded in standard medical terminology rather than the subject's own words.
- Whenever possible, the investigator should combine signs and symptoms that constitute a single disease entity or syndrome into a final diagnosis, if appropriate. For example, fever, cough, and shortness of breath may be reported as pneumonia, if that is the final diagnosis.
- Each AE is to be evaluated for duration, severity, seriousness, and causal relationship to the investigational drug. The action taken and the outcome must also be recorded.
- SAEs that occur during the study or within 28 days after last dose of study drug(s), whether related to study drug, must be immediately reported to the Sponsor/SAE designee. Clinical trial sites will enter SAE information directly into the EDC clinical database within 24 hours of knowledge of the event. After the 28-day reporting window, only SAEs assessed as related to study drug need to be reported.

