#### **6.1.5.1. Adverse Event Date Imputations**

In cases of incomplete dates for adverse events (AEs), the missing component(s) will be assumed as the most conservative value(s) to conservatively capture AEs with missing start dates as treatment-emergent AEs (TEAEs) unless TEAE status was disqualified based on a pre-treatment stop date/time. The imputation rules are as follows:

- If “day” is the only missing field, impute the “day” as the first randomized dose date if the month and year of randomization are equal to the AE start month and year; otherwise, impute the “day” as the first day of the AE start month.
- If “day” and “month” are missing, impute the “day” and “month” as the day and month of the first randomized dose date if “year” is the same as the year of randomization; otherwise, impute January 1 of the non-missing year.
- Missing time will not be imputed. If “time” is missing and the start date is the same as the first dose date, then the time is assumed to be after the first dose time so that the event will be classified as treatment emergent.
- If the start date is completely missing:
  - and from the end date (either complete or partial date) it cannot be deduced to be prior to the first dose date, then the AE will be assigned as a TEAE.
  - and from the end date (either complete or partial date) it can be deduced to be prior to the first dose date, then the AE will not be assigned as a TEAE.

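### The SAP defines a TEAE by onset alone, so an AE that starts before dosing and worsens on drug may go uncounted, although the protocol's definition includes exacerbations

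*SAP*

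**What the plan says.** SAP 6.11.1.1 sets the rule for every TEAE table: "TEAE is defined as an adverse event with an onset that occurs after receiving the first dose of the study drug", "and within 30 days after receiving the last dose of the study drug". Its formula compares the AE start date with the first and last dose dates. It does not mention a rise in grade, a rise in frequency, or an ongoing event becoming serious.

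Protocol 10.1.2 is wider. It covers any unfavorable sign, "symptom, or disease temporally associated with the use of an investigational product", and adds: "This includes an exacerbation of pre-existing conditions or events". It also says that expected fluctuation short of a clinically significant worsening is not an AE. Protocol 10.1.1 is consistent with this. Among the items that need not be recorded as AEs, if already listed as medical history, it names: "Pre-existing events that has not worsened in intensity or frequency from baseline". A worsened one is therefore recordable.

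Collection starts well before dosing. Protocol 10.2 states: "Any AE that occurs after signing of ICF through 28 days after last dose of study drug(s) should be recorded on the AE eCRF".

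Protocol 12.1 expects the SAP to set out changes to the planned analyses. SAP section 7 lists one, a supportive t-test on liver fat.

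**The concern.** TEAE incidence is a primary safety endpoint in both documents. Screening can open at C1/D-45, and every subject has a run-in from C1/D-14 with deuterated water, blood draws and sebum sampling. AEs with onset before the first dose are therefore to be expected on the AE eCRF. If one is still ongoing at C1/D1 and worsens on study drug, the protocol treats the worsening as treatment-emergent. The SAP rule looks only at when the event began.

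An event excluded in this way is lost from the general TEAE table and from the tables built on it: drug-related, serious, leading to discontinuation, and severity. The known effects of FT-4101 are on skin, hair and eye, and these have the weakest backup. SAP 6.11.1.3 only lists physical examination findings. A skin or eye event that rises to Grade 2 calls for dose interruption under Protocol Table 6-1, yet it could be missing from every TEAE table.

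**Working it through.** Neither document states an expected TEAE rate, so there is no plan figure to reproduce. The check applies the rule to example records and then works out the size per subject.

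**1. The rule.** A record is a TEAE if start date ≥ first-dose date and start date − last-dose date ≤ 30 days. In the examples the first dose is C1/D1 and the last is C4/D14. Every start date precedes the last dose, so the second condition always holds and only the first decides.

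**2. Example records (dates and grades are illustrative).**

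| Event | Recorded start | SAP rule | Protocol 10.1.2 |
|---|---|---|---|
| A. Dry skin, Grade 1 from C1/D-5, Grade 2 from C1/D10, kept on one record | C1/D-5 | Not a TEAE | TEAE, if more than anticipated fluctuation |
| B. Same course, worsening entered as a new record | C1/D10 | TEAE | TEAE |
| C. Medical-history condition that worsens and first becomes an AE on C1/D10 | C1/D10 | TEAE | TEAE |
| D. New dry skin on C1/D10 | C1/D10 | TEAE | TEAE |

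A and B are the same clinical course. They differ only in data entry. C shows that medical-history conditions are normally captured. The exposed group is therefore AEs first recorded between consent and first dose.

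**3. Does either document settle A against B?** No. Protocol 11.2.2 leaves data-entry instructions to the eCRF Completion Guidelines. The SAP's counting rule for repeated AEs takes one count per subject at the maximum grade. That handles several qualifying records, but it does not admit one with a pre-dose start.

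**4. Consistency within the SAP.** SAP 6.1.5.1 counts an AE with a wholly unknown start as a TEAE unless its end date shows that it finished before dosing. Event A, with a known start and a documented worsening on drug, is left out. That fits poorly with the section's stated aim of capturing events conservatively.

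**5. Size.** Let k be the number of subjects in an arm of n whose only qualifying event is of type A. The shortfall in any-TEAE incidence is 100 × k / n percentage points. Each active arm has n = 10 and pooled placebo is 5 + 5 = 10.

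- k = 0: 0 points
- k = 1: 100 × 1/10 = 10 points
- k = 2: 100 × 2/10 = 20 points

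The values of k are assumptions. In a preferred-term table the same arithmetic holds only if the subject has no other post-dose record of that term.

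**6. Direction.** Leaving out a worsening criterion can only lower counts, in any arm. If the drug causes the worsening, more of the loss would fall on the active arms.

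**The case against.** The strongest answer is that no event need be lost. The protocol treats the exacerbation itself as the event. If sites enter it with its own onset date, it meets the SAP rule. The eCRF Completion Guidelines may already require this. That stands, and it is why the conclusion is conditional.

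Three further points narrow the exposure without removing it:

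- Exclusion criteria 14 to 16 remove much recent skin, hair and eye disease. They do not prevent onset during the run-in.
- Laboratory worsening in the analytes named in SAP 6.11.1.2 would appear in the CTCAE shift tables, and all data are listed by subject. The shift tables do not cover skin, hair or eye findings.
- One row of the overall summary in SAP 6.11.1.1 refers to Grade 3 or higher AEs rather than TEAEs, so loss from that row is not established.

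A reader might infer more than the documents support, in three ways:

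- **That events are certainly dropped and incidence is certainly understated.** This depends on the recording convention, which neither document gives.
- **That the rule ignores time of day, so events before the dose on C1/D1 are counted.** The formula alone could be read so. But the sentence says after the first dose, and SAP 6.1.5.1 makes an assumption only where the time is missing: "then the time is assumed to be after the first dose time so that the event will be classified as treatment emergent". This implies that a recorded time is used.
- **That the escalation decision is affected.** The stopping criteria in Protocol 6.5.1 refer to AEs as judged by the investigator, not to the SAP's TEAE flag.

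**Conclusion.** The mismatch is real. The SAP applies an onset-only rule to a primary safety endpoint, the protocol's definition includes exacerbations, and the narrowing is not declared. TEAE incidence may be understated. The effect ranges from zero, if worsening is always entered as a newly dated record, to 10 percentage points of any-TEAE incidence per affected subject in a 10-subject arm. The upper figure assumes that the worsened event stays on its pre-dose record and that the subject has no other TEAE. The documents give neither a run-in AE rate nor a worsening rate, so the chance of this happening cannot be stated. It does not undermine the trial, but a primary endpoint should not depend on a data-entry convention that the plan does not state.

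**What to change.** In SAP 6.11.1.1, define a TEAE as either:

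1. an AE with onset after the first dose of IP; or
2. an AE with onset before the first dose that, after the first dose and within the stated window, worsens in severity or frequency beyond the anticipated fluctuation described in Protocol 10.1.2, or becomes serious.

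For events admitted under (2), tabulate the maximum post-dose grade.

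State how a post-dose worsening of an ongoing AE is recorded, either as a dated grade change on the existing record or as a new record dated at the worsening. Check first whether the eCRF Completion Guidelines already say so. If both routes end up in the data, the SAP's existing once-per-subject count within preferred term prevents double counting. If the sponsor prefers to keep the onset-only rule, SAP section 7 should list it as a departure from the protocol.

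The cost is a few lines of SAP text and perhaps one line in the guidelines. No new data are needed where grade changes are already dated; where they are not, queries should go out before database lock. TEAE counts may rise slightly in any arm, including placebo.
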